## ACCOUNTING FOR NON-COMPLIANCE

The study protocol intervention reports the procalcitonin results and guideline to the treating clinician. The first and primary measure of protocol compliance is intervention delivery. We define procalcitonin reporting compliance to have been achieved in those subjects whose key clinician received procalcitonin information at  $\geq 80\%$  of the protocol-specified timepoints (in the ED, and if hospitalized, 6-24h after the ED measurement, and on Days 3, 5, and 7 if still in hospital and on antibiotics). As the protocol intervention involves multiple time points, we defined compliance based on satisfactory rather than full adherence [36].

The study protocol stipulates clinicians have decision-making autonomy, and thus clinicians who act discordantly with the procalcitonin guideline are not in violation of the protocol. We do however aim to understand cases where clinicians choose actions congruent with the procalcitonin guideline, and term this scenario procalcitonin guideline care congruence. We define procalcitonin guideline care congruence to have been achieved in those subjects whose key clinician followed the procalcitonin guideline  $\geq 80\%$  of the time in the procalcitonin guideline arm. These criteria imply that congruence status is only observable in the intervention arm. If the clinician never received procalcitonin information at any of the time points, we exclude the subject from the congruence analysis since congruence status is unevaluable.

We will report frequency and rates of each compliance type. For procalcitonin guideline care congruence (or lack of congruence), we will also consider magnitude (e.g., antibiotic prescription despite a strong versus a simple guideline recommendation to withhold) and direction (e.g., antibiotic prescription despite guideline recommendation to withhold, versus antibiotic withholding despite recommendation to prescribe).

Under imperfect compliance in the procalcitonin guideline arm, an ITT analysis evaluates the effect of random assignment (effectiveness), not necessarily the effect of the intervention itself if received as intended (efficacy) [27, 37]. It can bias towards no difference, which may lead to a false rejection of H2o, which uses a noninferiority design. Hence, we will also perform a per-protocol analysis in the final look following CONSORT guidelines, focusing on compliance of procalcitonin reporting.

## **SECONDARY OUTCOMES ANALYSIS**

We will follow the analysis strategies used for the primary outcomes to compare the secondary outcomes between study arms. Both ITT and per-protocol analyses will be conducted. Differences in proportions for secondary binary endpoints (antibiotic initiation by initial ED physician, ICU admission, subsequent ED visits by Day 30) will be estimated along with 95% confidence intervals. Continuous secondary endpoints (hospital length of stay, quality of life) will be compared using two-sample t-test or Wilcoxon rank sum test. Mortality at 90-days and 1 year will be estimated using Kaplan-Meier. All analyses of the secondary outcomes are considered descriptive and no formal inferences will be drawn from the secondary outcome analyses.

## SUBGROUP ANALYSES

We will conduct prespecified subgroup analyses to understand the treatment effect, and to identify subgroups of patients for whom the treatment was particularly beneficial and/or harmful. These analyses will allow future hypothesis generation. The subgroups are predefined to limit bias. We will include subgroup analyses on lower respiratory tract infection subtype; ethnicity – Hispanic/Latino, race – African-American, White, other; gender – female, male; and age – below 65 years, 65 years and older.

## SENSITIVITY ANALYSES

The MAR assumption in imputing missing data is unlikely to bias findings for H2o, which uses a noninferiority design [38]. Sensitivity analyses will assess the robustness of study findings to missing data. We will conduct a complete-case analysis, which assumes that data are missing-completely-at-random (MCAR). We will also conduct a missing-not-at-random (MNAR) sensitivity analysis using control-based imputation in which all data are imputed based on the usual care arm. This assumes that the unobserved outcome in the procalcitonin arm would have been similar to what was observed in the control arm. It imputes an outcome almost certainly worse than that assumed by MAR [38], and is unlikely to positively bias the efficacy aim H1o.

Per-protocol analyses may suffer from selection bias [27]. As an alternative, we will use an instrumental variable approach to estimate the CACE. The CACE measures the impact of the intervention in the subgroup of the population that complies with the assigned intervention [29, 31]. It is a widely used complementary parameter of interest for treatment efficacy in randomized experiments [31]. The intervention assignment will be used as the instrument since

due to randomization, its impact on outcome is expected to be entirely mediated through the receipt of the intervention [33].

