**POWER AND SAMPLE SIZE**

The sample size was driven by the safety aim ( $H_2o$ ) due to the non-inferiority hypothesis and the binary nature of the outcome. The original sample size of 1,514 participants (757 per arm) was based on the differences in proportions in the composite adverse outcomes endpoint between the two arms. Our power calculations accounted for two interim analyses at approximately 1/3 and 2/3 enrollment with stopping boundaries calculated using the O'Brien and Fleming method,  $\geq 80\%$  power to reject  $H_2o$ , and a predefined 4.5% noninferiority margin. The noninferiority margin was chosen based on clinical meaningfulness and feasibility within funding constraints. It is approximately half that of the Infectious Diseases Society of America's recommendation and of two large trials of procalcitonin antibiotic guidance [10, 18].

We assumed 11% adverse outcomes by Day 30 in the usual care arm [19, 20] and a 10% loss to follow up for the original sample size estimate. We prospectively monitored both frequencies based on the overall blinded sample with intent to recalculate and adjust the sample size as necessary. The use of blinded data for the recalculation ensures that the overall significance level is 0.05. After approval by the DSMB in April 2017, the sample size was increased to 1,664 participants.

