## MISSING DATA

Despite best efforts to obtain follow-up data, we anticipated some loss-to-follow-up. Optimal ITT includes analysis of data from all subjects randomized and cannot be directly adopted in the presence of missing data [25]. A complete-case analysis may lead to loss of power, and bias may be introduced when missing is not completely at random [23]. To resolve, we chose multiple imputations [24] to conduct the ITT analyses.

We will describe the extent and reasons that data are missing, summarizing the proportion of patients with missing data for each outcome and by study arm and by site. We will compare baseline patient characteristics between those who have complete outcome data and those that do not.

Multiply-imputed datasets will be generated using multivariate imputation by chained equations, an approach designed for multivariate data that can accommodate mixed data types [34]. We will use predictive mean matching and logistic regression to impute continuous and binary outcomes, respectively. We will generate 100 imputed datasets to maintain power, although 3-5 imputed datasets are usually sufficient to obtain excellent results [35].

We assume that missing outcome data are missing-at-random (MAR) in that they can be imputed reasonably well from the observed study data. We will perform imputation based on the study arm the patient was assigned to. Auxiliary variables for the imputation model will include patient baseline variables (e.g, age, sex, race, comorbidity, and condition), key ED clinician type (i.e., attending, fellow/resident, physician assistant/nurse practitioner) and study site. We will also include available intermediate outcomes, such as 15-day data to impute 30-day missing data.

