## **ANALYSIS OF PRIMARY OUTCOMES**

For H1o, we will test the hypothesis that procalcitonin guideline implementation does not change antibiotic exposure by comparing the mean number of 30-day total antibiotic-days between the procalcitonin and usual care arms using a two-sample t-test, or a Wilcoxon rank sum test if data are non-normal.

For H2o, we will compare the difference in proportions of the composite adverse outcomes endpoint, relative to a 4.5% noninferiority margin, and construct a two-sided 95% confidence interval for the difference in proportions. We will declare noninferiority if the upper limit of the confidence interval is below 4.5%.

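### For the non-inferiority hypothesis H2, the only committed missing-not-at-random check shrinks an observed harm, and no delta-adjusted or tipping-point analysis is planned

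*SAP*

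**What the plan says.** The primary intention-to-treat analysis uses multiple imputation under missing at random (MAR), by assigned arm (SAP IV, Missing Data). The model uses baseline variables, clinician type and site, and "We will also include available intermediate outcomes, such as 15-day data to impute 30-day missing data". For H2, "We will declare noninferiority if the upper limit of the confidence interval is below 4.5" per cent (SAP IV, Analysis of Primary Outcomes).

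SAP IV, Sensitivity Analyses, adds two missing-data checks. One is a complete-case analysis. The other is the only missing-not-at-random (MNAR) analysis, a "sensitivity analysis using control-based imputation in which all data are imputed based on the usual care arm". The SAP explains: "This assumes that the unobserved outcome in the procalcitonin arm would have been similar to what was observed in the control arm". It describes the imputed outcome as "almost certainly worse than that assumed by MAR [38], and is unlikely to positively bias the efficacy aim H1o". On H2 it says only: "The MAR assumption in imputing missing data is unlikely to bias findings for H2o, which uses a noninferiority design".

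Protocol 2.B.ii.c lists weighted estimating equations, multiple imputation and/or pattern mixture models. It names no delta, range or hypothesis, and the SAP does not carry pattern mixture models forward. Neither document commits to a delta-adjusted, tipping-point or worst-case analysis.

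**The concern.** Control-based imputation is cautious for a superiority claim because it erodes an observed benefit. H2 points the other way. Giving lost procalcitonin patients usual-care risk assumes that they suffered no excess, and it dilutes any excess seen in followed patients. In that case the imputed outcome is better than under MAR, not worse. The SAP recognises this kind of problem for non-compliance, where it says of the intention-to-treat analysis: "It can bias towards no difference, which may lead to a false rejection of" the H2 null hypothesis. It does not apply the same reasoning to missing data.

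Part of the composite is obtained by telephone after discharge (SAP II, Primary Outcomes). Records, releases and listed contacts (Protocol 2.A.iii) recover some events of patients who cannot be reached, but not necessarily all. If the MAR and control-based results agree, a reader may conclude that the safety finding is robust to hidden harm. Control-based imputation does not test that.

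**Working it through.** **Inputs.** From the documents: margin 4.5 points, usual-care risk 11%, 10% loss and 757 per arm originally (SAP III, Power and Sample Size); 1,664 patients randomised 1:1, so 832 per arm (SAP Abstract); decision on the upper limit of the two-sided 95% interval. Equal loss in both arms is assumed unless stated.

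**The plan's sample size.** A fixed design at one-sided 0.05 with 80% power needs (1.645 + 0.842)² × 2 × 0.11 × 0.89 / 0.045² = 598 per arm, or 598/0.9 = 665 after loss. Simulating the H2 boundaries of SAP Table 2 (futility binding) with 757 × 0.9 = 681 evaluable per arm gives 80.8% power. The planned 1,514 is therefore reproduced.

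**Step 1: what control-based imputation does.** Let p_P and p_C be the observed risks and m the missing fraction.

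- MAR: D = p_P − p_C
- Control-based: D = [(1 − m)p_P + m p_C] − p_C = (1 − m)(p_P − p_C)

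Upper limits use Rubin's variance W + (1 + 1/100)B for the SAP's 100 imputations, with 832 per arm and 10% missing:

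| Observed excess (points) | MAR: D, upper limit | Control-based: D, upper limit |
|---|---|---|
| −2.0 | −2.0, 1.04% | −1.8, 1.25% |
| 0 | 0, 3.17% | 0, 3.16% |
| 1.0 | 1.0, 4.23% | 0.9, 4.10% |
| 1.35 | 1.35, 4.60% (fails) | 1.22, 4.44% (passes) |
| 3.0 | 3.0, 6.35% | 2.7, 6.00% |

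The largest observed excess that still passes is 1.26 points under MAR and 1.43 under control-based imputation. If procalcitonin looks better, control-based imputation does raise the limit, but the limit stays far from 4.5%.

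**Step 2: how often the two verdicts differ.** Simulated trials (100 imputations, 10,000 trials per cell) were pooled over true excesses of 0, 1, 2, 3 and 4.5 points:

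| Set-up | MAR passes that control-based fails | MAR failures that control-based passes |
|---|---|---|
| No covariates, random loss | 3 of 18,431 | 1,349 |
| Covariate model, risk-related loss | 153 of 18,041 | 1,534 |
| Half the lost patients' events known from records | 9 of 19,005 | 712 |
| Both | 130 of 18,771 | 830 |

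Control-based imputation overturns at most 153/18,041 = 0.85% of MAR passes, and it is the more lenient method each time. At a true 4.5-point excess it passes 2.7–3.1% of trials, against 2.5–2.6% under MAR.

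**Step 3: hidden harm (an assumed scenario).** Let followed procalcitonin patients have a 3.5-point excess and lost ones 13.5 points (risk 11 + 13.5 = 24.5%). The overall excess is 0.9 × 3.5 + 0.1 × 13.5 = 4.5 points, so non-inferiority is false. For complete-case analysis with 748.8 followed per arm:

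- SE = √[(0.145 × 0.855 + 0.11 × 0.89)/748.8] = 1.72 points
- a pass needs an estimate below 4.5 − 1.96 × 1.72 = 1.13 points
- the pass probability is Φ[(1.13 − 3.5)/1.72] = 8.4%, against a nominal 2.5%

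Over 20,000 simulated trials, MAR, complete-case and control-based imputation pass in 8.4, 8.4 and 9.9%. With half the lost patients' events known, the figures are 5.0, 8.4 and 5.3%. A scan point set at the true lost-patient risk passes in 2.2% and fails 1,234 of the 1,670 MAR passes.

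**Step 4: tipping point.** Each extra event among procalcitonin patients adds 1/832 = 0.12 point. At an observed excess of 0 the room is 4.5 − 3.17 = 1.33 points, or about 11 events. The variance also grows, and the full solution is a rise of 12.06 points in 83.2 lost patients = 10.0 events. At an excess of 1 point it is 2.41 points × 83.2 = 2.0 events. Across the four set-ups of Step 2 the counts are 9.9–10.6 and 1.8–2.6. At 757 per arm they are 8.0–8.5 and 0.8–1.3. At 17% usual-care risk (the actual rate that Protocol 2.A.v quotes from an earlier multicentre trial) the count at excess 0 is 5.4–6.0.

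**The case against.** The strongest reply is about weight. The shrinkage is 0.1 point per 1-point excess at 10% loss, the verdict changes only in a narrow window, and at a true difference of zero there is on average nothing to shrink. This is correct.

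The SAP offers control-based imputation as cautious for H1 and never calls it a stress test for H2. That is also fair. It leaves H2 with no MNAR analysis in the direction that matters, supported only by the statement that MAR is unlikely to bias it.

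The 10% loss may be too high for a 30-day endpoint: Protocol 2.B.ii.a describes it as an annual rate, and several recovery routes exist. Lower loss changes the tipping risk more than the tipping count. At an observed excess of 0, the lost-patient risk needed to tip is 23% at 10% missing, 37% at 5% and 56% at 3%, while the count stays between 10 and 11. At 1% missing it cannot tip. That is a useful result, and only the scan would show it.

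The hidden-harm scenario is chosen, not documented, and the simulations omit Day 15 data and clinician type. The SAP also commits to reporting missingness by arm and site and to comparing patients with and without outcomes. These reports help a reader judge plausibility but do not quantify its effect on H2. Complete-case results can differ from MAR when measured covariates predict loss, but they do not test unmeasured excess risk.

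Using the final H2 boundary of −1.71 in SAP Table 2 instead of the 95% interval raises the tipping counts to 13.3 and 5.2. The conclusion is the same.

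**Conclusion.** The concern holds. For H2 the only committed MNAR analysis is slightly more lenient than the primary analysis whenever procalcitonin shows an excess. No committed analysis examines lost procalcitonin patients doing worse than followed patients of either arm suggest. The leniency itself is minor. The untested direction matters more, because about 10 unseen events at an observed excess of 0, or about 2 at 1 point, would reverse the safety conclusion under the plan's own 11% and 10% with 832 per arm.

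The strata, the loss pattern, the half-known share and the 24.5% risk are assumptions, and actual missingness is not in the documents. The tipping risk should not be carried over to other settings: across the four set-ups it ranges over 19–29% at excess 0 and 10–20% at 1 point. The primary analysis and its decision rule are not in error. This is a worthwhile addition to the sensitivity analyses of the primary safety outcome.

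**What to change.** Keep control-based imputation as the MNAR check for H1, and state that its H2 result is not a stress test for harm. For H2, add text such as:

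> With usual-care outcomes imputed under MAR by the model above, the event risk of procalcitonin-arm patients whose composite is still unknown after medical records, releases and contacts will be raised above its MAR value in 1-point steps until the upper 95% limit reaches 4.5%. We will report the number of extra events and the corresponding risk, and show usual-care risk plus 4.5 points as one point on the scan. If the limit already exceeds 4.5% under MAR, or is not reached at 100% risk, we will say so.

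Qualify the sentence on MAR and H2, for example by adding: unless lost procalcitonin patients do worse than followed patients with the same covariates. Leave the primary decision rule unchanged.

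The cost is a few lines of SAP text and extra runs of imputation code already planned. The downside is that the non-inferiority claim may look less robust, and the clinical team must judge whether the tipping count is plausible.

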## **EXPLORATORY ANALYSES**

The instrumental variable approach could correct the selection bias in the per-protocol analysis if the bias stems from unmeasured confounders. However, if the bias was due to measured variables, propensity scores can be used to balance background characteristics facilitating a fair comparison between groups. We will also conduct a propensity score approach to estimate the CACE. To build the propensity score model for compliance, we will consider all available baseline variables of patients, key clinician characteristics, and site. We will then adopt the principal causal effect estimation method [28] to estimate CACE .

If antibiotic use differs between the two study arms, we will also explore ways to determine integrated measures of overall gains in decision-making accuracy due to the procalcitonin guideline. We will leverage the randomized design, which allows an assumption that the underlying rate of a given condition, even when not directly measured, is balanced at baseline between study arms.

## **V. CONCLUSION**

We described our approach to analyzing the data from ProACT prior to unblinding. This will enhance the utility of the reported results and allow readers to better judge the quality and credibility of the findings.

**TABLES****TABLE 1 – DATA COLLECTED AT EACH TRIAL STAGE**

Stage	Data collected
Pre-randomization	
 
Patient demographics and inclusion/exclusion criteria
 

Baseline	
 
Sociodemographics - age, sex, race, ethnicity, residence, employment status, baseline physical function
 
Comorbidities and medications - Charlson comorbidity index, and medications related to respiratory care
 
Respiratory history – onset of symptoms, respiratory symptoms, tobacco, chronic respiratory diseases
 
Severity of illness and laboratories: PSI, CURB-65; clinically obtained labs, pulse oximetry
 
LRTI categories 
 
CAP - new radiologic pulmonary infiltrate, and one or more of the following criteria: cough, <math>> 38.0</math> or <math>< 36.0^{\circ}\text{C}</math>, sputum production, dyspnea, tachypnea, rhonchi, wheezing, chills, chest discomfort, white blood cell count <math>> 10^{10}</math> or <math>< 4 \times 10^9</math> cells/L [10, 39, 40]
 
COPD exacerbation - past medical history of or consistent with COPD, and acute worsening dyspnea, cough, or sputum production [41]
 
 
 

	
iii. Asthma exacerbation - past medical history of or consistent with asthma, and acute worsening dyspnea, cough, wheezing, or chest discomfort [42-44]
 
iv. Acute bronchitis - acute onset of cough, lasting less than 3 weeks in the absence of underlying lung disease (no past medical history of or consistent with COPD or asthma) or new infiltrate on chest x-ray [8, 45]
 
v. Other
 
a. Other, LRTI - > 1 respiratory symptom (cough, sputum, dyspnea, tachypnea, chest discomfort), and > 1 auscultation abnormality (wheezing or rhonchi) or > 1 infection sign (> 38.0 or < 36.0°C, chills, or white blood cell count > <math>10^{10}</math> or < <math>4 \times 10^9</math> cells/L), that does not meet (i)-(iv) criteria [10, 40]
 
b. Other, non-LRTI - those that do not meet (i) - (v.a.) criteria

ED	
 
• Antibiotics prescribed – name, dose, route, time
 
• Therapeutics and diagnostics – mechanical ventilation, steroids, bronchodilators, diuretics, CT scans, and chest x-rays
 
• Disposition – home, observation unit, hospital admission (floor, stepdown, ICU)
 

Hospital follow-up	
 
• Antibiotics prescribed – name, dose, route, days
 
• Therapeutics and diagnostics – mechanical ventilation, steroids, bronchodilators, diuretics, radiologic tests
 
• Adverse outcomes – vasopressors/mechanical ventilation/new renal replacement therapy ever used, highest recorded creatinine, lung abscess/empyema, pneumonia diagnosed after enrollment (for non-CAP LRTI), date of discharge (length of stay), ICU admission
 
• Clinically obtained microbiology results
 
• Disposition – home, nursing home, rehabilitation facility, etc.
 
• 15-day and 30-day follow-up
 
• We used a structured interview process for vital status, antibiotic days, repeat ED visits/hospital admissions and reason, and quality of life.
 

Post-discharge survival	
 
• We are collecting 90-day and 1-year mortality data through a National Death Index (NDI) search or, for more recently enrolled subjects, by direct contact with the patient or their listed contacts. For NDI, there is a 2-year time lag before these data are available, so for patients enrolled near the end of the trial, we will perform primary analyses before their 1-year follow-up data are available, and a shorter follow-up will be handled with censoring.
 

[figure not shown]
**TABLE 2 – INTERIM ANALYSES T-VALUE STOPPING BOUNDARIES**

Interim	H1o		H2o		$\alpha$ – spending*
Look	Efficacy	Futility	Efficacy	Futility	
1	< -3.21	> 1.64	< -3.26	> 0.55	0.001
2	< -2.15	> -0.49	< -2.16	> -0.87	0.016
Final	< -1.70	> -1.70	< -1.71	> -1.71	0.034

\* Overall  $\alpha = 0.05$ ; Stopping boundaries represent one-sided tests for significance. Two-sided tests will also be conducted in the final analysis.

## FIGURES

FIGURE 1 – TRIAL OUTCOME SCENARIOS ON INTERIM LOOKS

